6.6 Early Withdrawal of Subjects

6.6.1 Withdrawal of Individual Subjects

Subjects can leave the study at any time for any reason if they wish to do so without any consequences or loss of benefits to which they are otherwise entitled. Subjects may be withdrawn from the study prior to expected completion for reasons such as safety concerns, failure to adhere to protocol requirements, subject consent withdrawal, etc.

Any data collected until the time of subject withdrawal may be included in the final data analysis. Information on the subject's withdrawal should be documented in the case report form and should include clear documentation of the reason for withdrawal to the Sponsor.

6.6.2 Follow-up for subjects withdrawn from study

None. There are no long term effects anticipated from participating in this study.

6.6.3 Replacement of individual subjects after withdrawal

In case a subject leaves the study prematurely, another volunteer may be recruited.

7 STUDY PROCEDURES

7.1 Subject's demographic information, vital signs, [REDACTED] and all specified parameters will be noted in the subject's Case Report Form.

7.2 Centroid sensor placement

[REDACTED] The sensors will then be turned on. [REDACTED]
[REDACTED] The duration of the study for each subject will be at least 8 hours each day of monitoring up to 16 hours. Sensors may be replaced after 8 hours of use on a subject. If the

RAMS0006: Calibration and Usability Validation of Patient Monitoring Device for Pressure Injury Prevention and Fall Detection
Version 2.0

sensor is removed for a procedure, surgery, x-ray, or other reasons, the sensor may be placed back on the subject depending on the subject's comfort or at the PI's discretion.

Study staff will also record the Root's displayed patient position.

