2.3 Risk/Benefits

Benefits: There will be no direct benefits to the enrolled subjects. Future benefits to subjects include effective pressure injury prevention (i.e., reduction in their occurrence and/or severity) and detection of hospital falls.

Centroid device risks: As with all wearable sensors, the Centroid sensor has a risk of thermal burn as there is a coin battery in the sensor. The coin battery used in the Centroid device is widely used in other commercially available medical devices for wearable monitoring applications. Masimo's design includes safeguards against thermal burn, and this risk is believed to be low. Sensors will be attached with a medical-grade, biocompatible adhesive. Marks may appear on the skin beneath the sensor due to adhesion for a long period (from several hours to days). The risk is believed to be low. The sensor transmits that data, after on-sensor processing, via a radio link to the host device.

SEDLine V2 sensor and V2 patient cable risks: All patient-contact materials, including the adhesive used in the design of the Masimo sensors, have been subjected to biocompatibility tests per ISO 10993-1 and results demonstrate that the materials are non-toxic, non-irritating, and non-sensitizing. The sensors have been evaluated for mechanical and electrical safety and the risks have been determined to be minimal. The modifications to the sensor are specifically designed so as not to introduce any new risks to the subject.

Pulse oximeter risks: The Radical-7 pulse CO-oximeter device and LNCS® pulse oximeter sensors used in this study are FDA-cleared.

Root patient monitoring system risks: The Masimo Root Monitoring System and SedLine brain function module used during this study are FDA-cleared devices.

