6.5 Subject Recruitment and Screening

Following identification of a potential subject, the patient will be approached by the principal investigator or a designated research staff member, who will explain the purpose and procedures of the study. If the patient expresses interest in participating in the study, they will be asked to read the written Informed Consent Form in English or Spanish depending on the patient's language preference.

All items of the Informed Consent will be explained in a way that is easily understandable, for either English or Spanish speaking subjects. The patient will be given adequate time to read through the Informed Consent, and they will be given adequate time and privacy to consider the decision of whether or not to sign the Informed Consent Form. Once all of the patient's questions have been answered and the Informed Consent Form signed, the patient is now adequately consented.

RAMS0006: Calibration and Usability Validation of Patient Monitoring Device for Pressure Injury Prevention and Fall Detection
Version 2.0

Now the patient will be enrolled as a study subject, at which time the subject will be assigned a study identification number or enrollment number.

All subjects will have their medical history reviewed at the time of screening by either the PI or the study staff who is delegated for this task. Subjects will be evaluated based on the inclusion and exclusion criteria to determine eligibility to be enrolled into the study. If a subject is deemed ineligible after screening, the subject will be withdrawn from the study.

Information regarding the subject's demographic (including, but not limited to age, weight, race, ethnicity, etc.), preexisting allergies, skin abnormalities, and other preexisting diseases/conditions that may be relevant to the study will be recorded within a paper-based Case Report Form (CRF).

HIPAA

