7.4 SedLine sensor placement

The SedLine sensor will be applied to the subject's forehead and data collection will be initiated on the Root monitor. The sensor may be removed at any time, depending on the subject's tolerance of the sensor.

7.5 The study will be terminated at the discretion of the PI if any significant adverse event is observed.

7.6 At the conclusion of the study, devices and data recording will be stopped and all sensors will be removed from the subject.

7.7 The skin will be inspected for any signs of redness or irritation.

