9 SAFETY AND ADVERSE EVENTS

9.1 Definitions

The definitions for adverse event, adverse device effect, serious adverse event, serious adverse device effect, and unanticipated adverse device effect are provided below (ISO 14155:2011, 21 CFR 812.3(s)).

- Adverse Event (AE): an adverse event is any untoward medical occurrence in a subject which need not be related to the device under investigation.
- Adverse Device Effect (ADE): an adverse device effect is any untoward or unintended response to a medical device which may result from insufficiencies in the instructions for use or deployment of the device, or from use error.
- Serious Adverse Event (SAE): a serious adverse event is an adverse event that results in death, inpatient hospitalization, severe or permanent disability, a life threatening illness or injury, fetal distress, fetal death, a congenital abnormality, a birth defect, or medical or surgical intervention to prevent permanent impairment to body or structure.
- Serious Adverse Device Effect (SADE): a serious adverse device effect is an adverse device effect that results in death, inpatient hospitalization, severe or permanent disability or is life threatening.
- Unanticipated Adverse Device Effect (UADE): any serious adverse effect on health or safety or any life threatening problem or death cause by or associated with, a device, if the effect, problem, or death was not previously identified in

nature, severity or degree of incidence in the investigational plan, or application (including a supplementary plan or application) or any other unanticipated serious problem associated with a device that related to the rights, safety or welfare of subjects. Refer to the Device Risk Analysis and Risk Assessment section for details on anticipated adverse device effects.

9.2 Anticipated Adverse Events:

Sensor may cause slight, temporary redness, which should fade away shortly after sensor removal.

Sensor may cause thermal burn; however, the design includes safeguards and this risk is believed to be minimal. There may be mild allergic reaction to sensor material and adhesives.

9.3 Adverse Event Reporting:

- All Adverse Events, both Anticipated and Unanticipated, must be recorded in the within the CRF and in the Adverse Event Report Form.
- All Adverse Events must be promptly reported to the Sponsor.
- All Unanticipated Adverse Device Effects will be also reported to both the Sponsor and the IRB.

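### In the readable text the only skin inspection follows final sensor removal, so slight transient redness from a Centroid wear that ends mid-study can go unrecorded

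*Combined protocol and SAP*

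**What the plan says.** **Mid-study removal.** Section 7.2 permits two events that end a wear before the study ends. The first is replacement: "Sensors may be replaced after 8 hours of use on a subject". The second is temporary removal for a procedure, surgery, imaging or another cause, after which "or other reasons, the sensor may be placed back on the subject". Putting it back turns on the subject's comfort or the investigator's discretion. Section 6.4 sets participation at roughly 8 to 16 hours.

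**Inspection.** Item 7.6 reads: "At the conclusion of the study, devices and data recording will be stopped and all sensors will be removed from the subject". Item 7.7 follows at once: "The skin will be inspected for any signs of redness or irritation". Item 7.7 gives no time, and no other readable sentence calls for a skin inspection.

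**Expected skin effects.** Section 2.3 warns of marks under a sensor worn for hours or days. Section 9.2 lists mild, passing redness "which should fade away shortly after sensor removal", and also mild allergic reaction and thermal burn.

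**Recording.** Section 9.3: "All Adverse Events, both Anticipated and Unanticipated, must be recorded". Section 6.5 says that at enrollment "preexisting allergies, skin abnormalities, and other preexisting diseases/conditions that may be relevant to the study will be recorded". Section 13.1 adds a general statement that subjects will be closely monitored.

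**The concern.** The plan names passing redness as an anticipated adverse event and requires every anticipated event to be recorded. For a wear that ends mid-study, however, the readable procedures schedule no look at the skin while such redness would still be visible. The weakness is in how events are found, not in the reporting rule: Section 9.3 works only on what someone has seen.

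Two things follow. Slight skin reactions to the investigational sensor may be under-counted. And the readable put-back sentence does not make reapplication depend on the state of the skin, although the plan itself attributes adhesive and burn risks to the sensor. Section 2.3 says that subjects gain no direct benefit, which favors inexpensive protection.

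**Working it through.** The plan gives no sample-size, power or event-rate figure on this point, so there is nothing to reproduce. The check sets the sections side by side and works out one time interval.

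**Step 1: when does the listed inspection happen?** Item 7.7 has no time of its own. Its place directly after item 7.6 makes the end of the study the natural reading. This is an inference from position.

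**Step 2: which wears does it follow?** Let *T* be the hours monitored and *t* the hour at which a sensor comes off. With continuous monitoring, the gap from that removal to the final check is *T* − *t*.

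| Case | *T* (h) | *t* (h) | Gap *T* − *t* (h) | Wears | Listed inspections |
|---|---|---|---|---|---|
| Minimum stay, no removal | 8 | 8 | 8 − 8 = 0 | 1 | 1 |
| Maximum stay, replacement when first allowed | 16 | 8 | 16 − 8 = 8 | 2 | 1 |

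The 8 and 16 hours come from Sections 6.4 and 7.2. In a 16-hour subject, a sensor taken off before hour 8 and put back gives a gap of more than 8 hours. Any time off the sensor adds to the elapsed gap. Each further removal and reapplication adds one wear and no listed inspection.

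**Step 3: would redness still be visible?** Section 9.2 expects it to fade shortly after removal, without saying how long that is. On the plan's own description, redness from the first wear is not expected to be visible about 8 hours later. If the same site is used again, a finding at the end cannot be assigned to one wear or the other. The readable text does not say whether the site changes.

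**Step 4: does another readable provision supply the missing look?**
- Sections 2.2.4, 6.6.1, 7.5, 9.3 and 14 cover deficiencies, withdrawal, termination, reporting and evaluation of events. They act once something has been noticed.
- Section 13.1 is continuing surveillance, but it is not specific to skin and gives no schedule.
- Section 7.2's comfort and discretion condition allows a check before put-back but does not require one.
- Section 6.5 records pre-existing skin abnormalities as background. It does not describe examining the sensor site.

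None of these is an instruction to inspect the skin when a sensor comes off mid-study or before it goes back on.

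**The case against.** The strongest reply is that this argues from silence in a redacted section. Section 7.2 has redacted blocks before the replacement and put-back sentences, in the placement steps where a skin check could well sit. Section 7.1 has a redacted item among those noted on the CRF, and the text between Sections 4.2 and 6 was not available. This stands as a limit. A reader might infer that sensors are put back on skin that nobody has been told to inspect; the documents do not support that, because the instruction could lie in text that cannot be seen. What can be said is that the two readable sentences contain no check.

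Second, item 7.7 has no stated time, and item 7.5 in the same list can apply at any moment, so list order does not settle timing. This also stands in part. The end of the study is the likelier reading, not the only one. If every removal is meant, one clause would say so.

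Third, anyone reapplying an adhesive sensor will probably see the skin, subjects are under general monitoring, and the investigator may decline to put the sensor back. This lowers the chance of a miss but does not require anyone to look or to record the finding.

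Fourth, the consequence is small. Replacement is optional, and a subject who completes at 8 hours may have a single wear. According to Section 4.2, the calibration phase has no endpoints, and the readable validation endpoint is a user questionnaire. This stands in full.

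**Conclusion.** The point holds as an optional, low-cost improvement. On the readable text, slight transient redness from a wear that ends mid-study can go unrecorded, and put-back rests on comfort or investigator discretion, with only general monitoring behind it. The word is *can*, not *will*: staff who happen to see redness are already bound to record it.

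**Size.** In the 16-hour illustration the gap is about 8 hours, with two wears and one listed inspection. The readable plan gives neither the number of mid-study removals nor a skin-event rate, so no count of missed events is offered.

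**Assumptions.** The conclusion assumes that item 7.7 applies at the end of the study, that redness fades as Section 9.2 expects, and that no inspection is required in the redacted or unavailable text. If one is required there, the point is answered.

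Two further readings go too far. A reader might infer that serious skin harm would be missed; a burn or lasting allergic reaction would more likely still be seen at the final check, so the loss is mainly slight redness. A reader might also infer that the study's results are compromised; no readable endpoint uses a skin-event count.

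**What to change.** First confirm from the unredacted text whether an inspection at each removal is already required. If it is not:

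- Keep item 7.7, which also covers the other sensors at study end, and add: *The skin under the Centroid sensor will be inspected for redness or irritation, and the finding recorded on the CRF, at every sensor removal (or, if clinical staff removed it, before reapplication) and before any sensor is applied or reapplied.*
- Add to Section 7.2: *A sensor is not put back on skin showing a suspected burn or allergic reaction.* This turns what investigator discretion already allows into a plain rule.

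The look before first application supplies the sensor-site baseline. Section 6.5 should not be relied on for that.

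**Cost.** Two sentences in an amendment, one CRF line per removal, and possibly a few lost monitoring hours where a sensor is not put back. No extra subjects are needed. One gap remains: when clinical staff take the sensor off, study staff may first see the skin some time later, and brief redness may already have faded.

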7.3 LNCS Pulse oximeter sensor placement

The LNCS pulse oximeter sensor may be placed on the subject's finger. The data collection will be initiated on the Root monitor. The sensor may be removed at any time, depending on the subject's tolerance of the sensor.

7.4 SedLine sensor placement

The SedLine sensor will be applied to the subject's forehead and data collection will be initiated on the Root monitor. The sensor may be removed at any time, depending on the subject's tolerance of the sensor.

7.5 The study will be terminated at the discretion of the PI if any significant adverse event is observed.

7.6 At the conclusion of the study, devices and data recording will be stopped and all sensors will be removed from the subject.

7.7 The skin will be inspected for any signs of redness or irritation.

8 SAMPLE SIZE AND STATISTICAL CONSIDERATIONS

8.1 Calibration and Validation stage

The calibration stage will continue until a sufficient number of cases have been obtained with quality data (e.g. no data drop-outs). Initial data sets may be considered training sets and may not be used for device calibration. Documentation will be included in the study records of when the calibration stage has concluded and when the validation stage commenced.

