1.2 Investigational Devices

RAMS0006: Calibration and Usability Validation of Patient Monitoring Device for Pressure Injury Prevention and Fall Detection
Version 2.0

The Centroid device is a non-invasive body-worn investigational device that is intended to detect the positional changes and physical movements of a subject. The device mainly consists of [REDACTED] Bluetooth LE radio, and a coin-cell lithium battery. The Centroid device is a disposable sensor that is capable of adhering to a subject's skin and continuously storing and transmitting positional data wirelessly, to a host instruments/devices to analyze the subject's activities. The sensor's skin-contacting materials are biocompatible and are thermally non-conductive. The device is intended to be used in hospitals, hospital-type facilities, healthcare facilities, and home environments.

Investigational SedLine sensors and patient cables may be used in this study. The SedLine brain function module is non-invasive and uses sensors that adhere to the subject's forehead. The SedLine brain function module uses a sophisticated multivariate algorithm to assess the patient's electroencephalogram (EEG) data from all 4 channels of the SedLine EEG sensor. The SedLine V2 sensor is intended to monitor the state of the brain by real-time data acquisition and processing of EEG signals. The SedLine system includes patient cable that connects the sensor and module to the Root multi-function monitoring system, which monitors multiple physiological parameters in healthcare environments.

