3 STUDY OBJECTIVES

The primary aim of this study is to collect data for *calibration* and *usability validation* of the new Centroid monitoring system which Masimo has developed for monitoring a patient's position and movement to prevent pressure injury and detecting falls in the hospital. This protocol describes data collection from patient volunteers during their routine hospital stay lasting usually for more than one day. During the calibration phase, positional data will be collected for the purpose of evaluating the Centroid design and technology.

Secondary aims are to collect data for the pulse oximeter sensor and SedLine sensor for the purpose of correlating against Centroid sensor's data and further investigation.

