6.4 Study Timelines

Each individual subject may participate in this study from approximately 8 hours to 16 hours. Data collection may start only after the informed consent has been signed by the participant. The subject will be considered to have completed the study after at least 8 hours of Centroid data have been collected. The study is expected to be completed within 12 months of initiation.

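### Must section 8.1 fix in advance which calibration cases count, how many are enough, and what a drop-out is?

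*Combined protocol and SAP*

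**What the plan says.** Section 8.1 governs the calibration data set in three sentences. The stopping rule is "The calibration stage will continue until a sufficient number of cases have been obtained with quality data (e.g. no data drop-outs"). Next, "Initial data sets may be considered training sets and may not be used for device calibration". Finally, "Documentation will be included in the study records of when the calibration stage has concluded and when the validation stage commenced".

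Other sections bear on what a usable recording is:

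- **6.4** sets completion: "The subject will be considered to have completed the study after at least 8 hours of Centroid data have been collected". It does not ask for the hours to be continuous. Participation may run from about 8 to 16 hours.
- **7.2** allows "Sensors may be replaced after 8 hours of use on a subject". It also says that if the "sensor is removed for a procedure, surgery, x-ray, or other reasons, the sensor may be placed back on the subject", subject to comfort or the investigator's discretion.
- **1.2** describes the sensor as "continuously storing and transmitting positional data wirelessly", so a radio gap need not mean lost data.
- **Section 3** gives the purpose: "During the calibration phase, positional data will be collected for the purpose of evaluating the Centroid design and technology".
- **4.2** states that the data collection and calibration phase has no endpoints.
- **6.1 and 8.2** give the only sample-size figures, both minimums: 60 subjects in total and 30 for usability validation.

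**The concern.** Three choices that shape the calibration set are left open in the visible text: what makes a case good enough, how many such cases suffice, and how many early sets may be treated as training material. All three can be settled after the data have been seen.

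The one example given, absence of drop-outs, is also hard to apply. In ICU patients, the removals and replacements that 7.2 permits are foreseeable, and 8.1 does not say whether they count. A 16-hour recording with one replacement at 8 hours holds twice the minimum in 6.4 (16/8 = 2), yet the text does not say whether it is a calibration case.

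If only the counted cases were ever described, a reader could not tell a sensor that nearly always records cleanly from one that loses half its recordings. Section 2.2.4 treats poor reliability or performance as a device deficiency, so such losses are information about the device. Calibration is one of the two parts of the primary aim, which makes the silence look more serious.

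**Working it through.** **1. Is there a figure to reproduce?** No. The documents give no calibration count, drop-out rate, precision target, alpha or power. Subtracting the two minimums gives 60 − 30 = 30. Both figures are floors, so this remainder is neither a minimum nor a maximum for calibration.

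**2. What could the open definition change?** Let k be the number of counted cases and p the share of monitored recordings that qualify. Both are assumptions. The expected number monitored is N = k/p. With k = 30:

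| p (assumed) | N = 30/p | Not counted, N − 30 | N plus 30 for validation |
|---|---|---|---|
| 0.9 | 33.3 | 3.3 | 63.3 |
| 0.7 | 42.9 | 12.9 | 72.9 |
| 0.5 | 60 | 30 | 90 |

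Rounded up to whole patients, N is 34, 43 or 60, and the totals are 64, 73 or 90. All satisfy the minimum of 60 in 6.1, so the enrollment figures do not reveal p. But the uncounted share is simply 1 − p, the assumption restated. Nothing here measures an effect on the calibration itself.

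**3. Which planned result would be affected?** In the visible text, section 3 frames the aim as collecting data for calibration and usability validation. Section 4.2 gives calibration no endpoint. The only analysis described is of a user questionnaire in the validation stage, and 8.2 confirms that this stage concerns usability only. No visible passage plans an estimate of accuracy, reliability or data loss from calibration recordings. The choice of cases therefore has no estimate, interval or test to bias.

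**4. Do 6.4 and 8.1 conflict?** Section 6.4 says when a subject has finished taking part. Section 8.1 says which data are useful for tuning the device. A subject can complete the study and still supply a recording unsuited to calibration. The drop-out wording in 8.1 is introduced as an example, does not bar recordings with gaps, and may mean signal or radio loss rather than removal of the sensor. Nothing in 7.2 contradicts it.

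**5. Can the number monitored be recovered?** Section 8.1 itself promises to record only the stage boundary, but other sections cover more:

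- 2.2.2 requires device and sensor use to be documented on case report forms for each subject.
- 2.2.4 requires all device deficiencies to be recorded and reported to the sponsor.
- 11.3 requires a case report form for each enrolled subject, including those who do not complete, covering device readings and deficiencies and giving the reason for any withdrawal.
- 11.4 has device data transferred to the sponsor, with read-only access for the engineers who analyze them.

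The number monitored, and the losses that amount to deficiencies, can therefore be reconstructed whatever number is finally counted.

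**The case for a change.** The strongest reply is that the absence of a test removes any argument about power but not the need to say which recordings shaped the device and which were left out. Section 3 does give calibration a purpose, evaluating the design and technology, and data loss bears on it. No visible passage requires a list of calibration cases not counted, with reasons. Section 6.6.1 also lets partial data from withdrawn subjects into the final analysis, so a partial recording might be used while a completed one with a gap is not. Writing the definitions down would need no extra patients or procedures.

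Part of this stands. The visible text of 8.1 is thin, and a sentence saying what makes a case usable would make the records easier to read. But the harm depends on a report that shows only counted cases, and no passage plans one. Selection after seeing the data cannot be ruled out, but neither is any bias shown. Fixing a sufficient number in advance is debatable in device development, where the amount of data needed is often learned along the way. Defining quality by time segment would also change the unit that 8.1 uses, which is the case. The open wording is a fair trade of precision for flexibility at this stage.

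**Conclusion.** The observation is accurate, but it describes undefined detail in a development stage, not a flaw that leads to a wrong estimate or conclusion. Followed as written, the plan yields a calibrated device and a usability questionnaire. Neither rests on a statistic that the choice of calibration cases could distort, and the per-subject records already required allow the number monitored to be recovered. Sections 6.4, 7.2 and 8.1 serve different purposes and do not contradict one another.

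The documents do not allow the size of any effect to be stated. The 33, 43 or 60 patients above rest wholly on the assumed 30 counted cases and the assumed qualifying shares.

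The conclusion rests on the visible text. Parts of 4.2, 7.2 and 11.4 are redacted and may hold definitions of gaps or quality, or further planned analyses. If the sponsor later drew a performance or reliability claim from the calibration recordings, that claim would need its own denominator and an account of exclusions. The visible plan makes no such claim, so no change to it follows.
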